#### **9.1.1.2 Recording Adverse Events**

All AEs must be recorded in the site's clinical trial records and the AE electronic CRF. Investigators should use correct medical terminology when recording events and avoid abbreviations.

The investigator should attempt to establish a diagnosis of the AE based on signs, symptoms, and/or other clinical information. The diagnosis, and not the individual signs/symptoms, or laboratory abnormalities, should be documented in the subject's source documents and the CRF unless the etiology of the event is unknown. If signs/symptoms cannot be medically characterized as a single diagnosis or syndrome at the time of reporting, each individual event should be recorded as an AE. If a diagnosis is subsequently established, it should be reported as follow-up information.

An assessment should be made at each visit (or more frequently if necessary) of any changes in severity, the suspected relationship to IP, the interventions required to treat it, and the outcome.

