### 9.1.2 Treatment-Emergent Adverse Events

A TEAE is defined as an AE that occurred during the clinical trial after the first dose of IP or was present prior to dosing, and exacerbates after the first dose of IP.

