5.2 Safety Population

Safety Population includes all randomized subjects who use at least one dose of investigational drug (Reproxalap Ophthalmic Solution or Vehicle Ophthalmic Solution), regardless of whether clinical trial assessments were performed.

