7.2 Adverse Events

AEs will be coded using the Medical Dictionary for Regulatory Activities (MedDRA) coding dictionary [REDACTED] preferred term (PT) and system organ classification (SOC).

An AE will be considered treatment emergent (TEAE) if it begins or worsens in severity after the first dose of the study drug through 30 days after the last dose of study drug, or the date of initiation of another investigational agent or surgical intervention.

Drug-related TEAEs are defined as definitely related, possibly related, or probably related to study drug. Any AEs with missing relationship to study drug will be considered as related to study drug.

All TEAEs with start dates prior to first dose date in Visit 4 EEC Treatment Session will be classified as AEs occurred in Visit 3 EEC Treatment Session.

An overall summary for number of subjects with events in each treatment will be provided including:

- Number of subjects with at least one TEAE
- Number of subjects with at least one Ocular TEAE
- Number of subjects with at least one drug-related TEAE
- Number of subjects with at least one drug-related Ocular TEAE
- Number of subjects with at least one serious TEAE
- Number of subjects with at least one serious Ocular TEAE
- Number of subjects with at least one TEAE leading to study discontinuation
- Number of subjects with at least one Ocular TEAE leading to study discontinuation

An AE is classified as an ocular AE if system organ class is coded as eye disorders.

The following types of summary for each treatment will be provided. Summaries will be sorted by decreasing frequency of PT within SOC which will be sorted alphabetically.

- TEAEs by SOC and PT
- Ocular TEAEs by SOC and PT
- Non-Ocular TEAEs by SOC and PT
- TEAEs by Casualty, SOC and PT

- Ocular TEAEs by Casualty, SOC and PT
- Non-Ocular TEAEs by Casualty, SOC and PT
- Serious TEAE by SOC and PT
- Ocular Serious TEAE by SOC and PT
- Non-Ocular Serious TEAE by SOC and PT
- TEAE by SOC, PT and maximum Severity
- Ocular TEAE by SOC, PT and maximum Severity
- Non-Ocular TEAE by SOC, PT and maximum Severity
- TEAEs leading to study discontinuation by SOC and PT
- Ocular TEAEs leading to study discontinuation by SOC and PT
- Non-Ocular TEAEs leading to study discontinuation by SOC and PT

If a preferred term or system organ class was reported more than once for a subject, the subject would only be counted once in the incidence for that preferred term or system organ class.

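### SAP 7.2 assigns adverse events to a session by start date alone, so worsening after the Visit 4 dose is missed for the Visit 4 product

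*SAP*

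**What the plan says.** SAP section 7.2 contains two rules that work together.

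- **What is treatment-emergent.** An AE qualifies when it meets this test: "begins or worsens in severity after the first dose of the study drug through 30 days after the last dose of study drug". (An alternative end point is also given; it does not matter here.) No session is named. SAP section 5.2 counts either product as study drug ("at least one dose of investigational drug (Reproxalap Ophthalmic Solution or Vehicle Ophthalmic Solution"), so for a subject dosed at both visits the anchor is the Visit 3 dose.
- **Which session it belongs to.** "All TEAEs with start dates prior to first dose date in Visit 4 EEC Treatment Session will be classified as AEs occurred in Visit 3". The rule covers all treatment-emergent events, looks only at the start date, and makes no exception for an event that qualifies through worsening.

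Section 7.2 then tabulates by product: "An overall summary for number of subjects with events in each treatment will be provided including". Its severity tables keep the worst grade per subject.

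Protocol section 9.1.2 has the same whole-trial anchor and explicitly admits an event that "was present prior to dosing, and exacerbates after the first dose of IP". Protocol section 10.8 agrees. On recording, Protocol section 9.1.1.2 says "An assessment should be made at each visit (or more frequently if necessary) of any changes in severity", but not whether a change updates the existing record or opens a new one. Among the items listed per event, Protocol section 9.1.1.3 includes start and end dates and times, but no date of worsening.

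**The concern.** In a two-period crossover, the session to which an AE is assigned decides which product carries it. The first rule admits events because they worsened; the second ignores when they worsened. An event can therefore be treatment-emergent only because of what followed the Visit 4 dose and still be counted against the product given at Visit 3. In sequence BA (vehicle first), a worsening after reproxalap would appear in the vehicle column. In sequence AB the reverse would happen.

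Safety is part of the primary objective, and the by-treatment AE tables are a main output for it. The events at risk of misplacement are the exacerbations that the definition was written to include.

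**Working it through.** The documents give no AE rate, so there is no planned figure to reproduce. The check applies the rules to each pattern of onset and worsening.

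**Inputs**
- Sequences AB and BA, 1:1, about 63 subjects each (SAP section 2.3.1). A is reproxalap and B is vehicle.
- Visit 4 at least two weeks after Visit 3 (SAP section 2.1). Assumed dosing days for the check: Visit 3 = day 0, Visit 4 = day 14.
- AEs collected from consent (Protocol section 9), so an AE can be on record before the Visit 3 dose.
- SAP rule: treatment-emergent if onset or worsening follows the Visit 3 dose; session decided by onset date.
- Comparison rule: each onset or worsening belongs to the session whose dose most recently preceded it.

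| Onset | Worsening | SAP 7.2 | Comparison rule |
|---|---|---|---|
| Before Visit 3 dose | None | Not treatment-emergent | Not treatment-emergent |
| Before Visit 3 dose | Between doses | Visit 3 | Visit 3 |
| Before Visit 3 dose | Only after Visit 4 dose | **Visit 3** | **Visit 4** |
| Between doses | None | Visit 3 | Visit 3 |
| Between doses | Only after Visit 4 dose | **Visit 3** | **Visit 3 and Visit 4** |
| After Visit 4 dose | None | Visit 4 | Visit 4 |
| Worsening entered as a new record dated after Visit 4 dose | n/a | Visit 4 | Visit 4 |

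The rules differ in two rows, and for different reasons. In the first bold row the event is placed under the wrong product. In the second the onset is placed correctly, but the worsening is not counted for the Visit 4 product and its grade enters the maximum-severity table under the Visit 3 product. The last row shows that the discrepancy disappears if a worsening gets its own record.

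**Effect on totals (first bold row).** Let *a* be the number of such subjects in AB and *b* the number in BA.
- SAP 7.2: reproxalap *a*, vehicle *b*.
- Comparison rule: reproxalap *b*, vehicle *a*.
- The reproxalap-minus-vehicle difference is *a* − *b* under the SAP and *b* − *a* under the comparison rule.

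Illustrations with assumed counts:
- *a* = 3, *b* = 3: 3 v 3 under both rules, so no net change.
- *a* = 2, *b* = 5: the SAP shows reproxalap 2, vehicle 5 (difference 2 − 5 = −3). The comparison rule gives reproxalap 5, vehicle 2 (difference 5 − 2 = +3).

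These counts show the mechanism only and do not estimate its size.

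**The case against.** **It depends on a recording convention that the documents do not show.** If the CRF instructions open a new record at each worsening, the start-date rule works. This stands, and the conclusion is conditional on it. But neither document states such a convention, and the SAP should not rely on one that it does not state.

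**Few events can follow the first pattern.** Protocol section 9.1.1.1 does not treat a condition present before Visit 2 as an AE unless it worsens, so its natural AE start date is the date of worsening. What remains is mainly an AE that starts between Visit 2 and the Visit 3 dose, is still on record at Visit 4, and worsens only then. This stands and narrows the point. It does not empty it: Visit 2 is itself a pollen challenge, and Visit 4 repeats the challenge.

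**An onset between the doses belongs to Visit 3.** Correct. A reader might infer that every AE worsening after the Visit 4 dose is charged to the wrong product. That is true only of the first pattern; in the second, what is lost is the additional count and the correct placement of the later severity.

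**The reach is limited.** A reader might infer that all safety tables are affected. SAP section 7.4 summarises vital signs by visit, and section 7.1 sets out the eye examinations by eye and side before and after chamber entry; neither uses the AE session rule. The discontinuation tables are barely touched, because Visit 4 is the exit visit. All AEs are also listed for the Safety Population, which allows case review but does not correct the tables.

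**Nothing shows that totals are distorted.** This stands. The documents do not support a claim that the AE comparison is wrong overall or that reproxalap's AEs are understated. With equal numbers in the two sequences, the first-pattern errors cancel in the totals, although each event is still misplaced.

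**Conclusion.** On the text as written, and provided that a worsening stays on its original record, SAP 7.2 gives a wrong attribution for one narrow pattern and an incomplete one for another. The affected outputs are the by-treatment incidence, severity and causality tables for AEs. The redaction in section 7.2 sits in the sentence on coding and gives no sign of hiding a session-specific rule.

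The frequency cannot be derived from the documents and is probably low. For the first pattern, treatment totals shift only if the sequences differ. With 1:1 allocation, a real product difference in exacerbations is one way in which they would. No efficacy claim is touched. The case for acting is that a stated rule gives the wrong answer for a class of events that the definition deliberately admits, and that the correction is cheap.

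**What to change.** Amend SAP section 7.2 before database lock, in one of two ways.

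1. **Session-specific definition.** An AE is treatment-emergent for a session if it starts after that session's first dose, or rises after that dose above its severity just before it. Assign it by the date of onset or worsening. An AE that worsens after the Visit 4 dose counts for the Visit 4 product at the worsened grade. It also counts for the Visit 3 product only if it began or worsened between the two doses, at the grade reached before Visit 4 dosing.
2. **Simpler alternative.** State that a worsening after the Visit 4 dose is handled as a new AE with its own start date and severity. The existing start-date rule then gives the right session. If the CRF instructions already require this, the SAP need only say so.

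The cost is a few sentences and minor AE programming. The date of worsening must be available, which may need an added field, although severity changes are already to be assessed at each visit. One AE may then appear under both products, and a table footnote should say so.

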## **10.3 Sample Size**

Approximately 670 subjects with ragweed-induced, moderate-to-severe allergic conjunctivitis will be screened in the EEC in order to randomize approximately 126 subjects, and for 100 subjects to complete the study. Approximately sixty-three (63) subjects will be assigned to each of two (2) treatment sequences, AB and BA.

Prior to database lock, the Sponsor will finalize a statistical analysis plan (SAP) that will detail all planned analyses and will dominate any statistical analysis herein. Any analyses conducted in addition to those specified in the SAP will be clearly documented as post hoc.

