## **10.8 Safety Analysis**

Adverse events will be coded using the MedDRA dictionary.

Frequencies and percentages will be provided per treatment group of subjects with treatment-emergent adverse events (TEAEs), serious TEAEs, and TEAEs causing premature discontinuation. An adverse event is treatment-emergent if it occurs or worsens after the first dose of randomized study treatment. Furthermore, frequencies will be given of subjects with TEAEs by system organ class, by system organ class and preferred term, by system organ class, preferred term and maximal severity, by system organ class, preferred term and strongest relationship, and by system organ class, preferred term, maximal severity, and strongest relationship. Separate analyses will be performed for ocular specific and all adverse events (including systemic).

Other safety endpoints including visual acuity, slit lamp biomicroscopy, intraocular pressure (IOP), tear osmolarity and dilated fundoscopy will be summarized by treatment group and visit using descriptive statistics. Changes or shifts from baseline will also be summarized where appropriate. For assessments performed by eye, worst eye (study eye) and fellow eye will be summarized separately.

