At all EEC sessions, assessments of ophthalmic evaluations will be collected [REDACTED]. [REDACTED]. In the event of an [REDACTED] failure, paper diary cards will be used as a back-up to collect symptom scores. For subject-reported symptoms of ocular itching, a standard 9 point (i.e., 0-4 with 0.5 unit increments) scale will be employed. For staff-assessed grading of conjunctival redness, a standard 9-point (i.e., 0-4 with 0.5 unit increments) will be employed. [REDACTED]

[REDACTED]

At the **EEC Screening Visit (Visit 2)**, qualified site staff will update concomitant medications and collect AEs, as applicable and perform tests for vital signs. A urine pregnancy test will be administered to WOCBP. Fundus exam, Snellen VA, SLE, subject rating of symptoms, and staff grading of conjunctival redness will be performed to ensure the anterior segment of the eye is healthy. [REDACTED]

Visit 2 Pre-EEC entry (Baseline):

- 1) Subject assessment for ocular itching and tearing will be recorded [REDACTED], and [REDACTED]
- 2) Staff-assessed conjunctival redness will be recorded [REDACTED].

Visit 2 Post-EEC entry:

- 1) Subject assessment for ocular itching and tearing will occur [REDACTED].
- 2) Staff-assessed conjunctival redness will be recorded [REDACTED].

[REDACTED]

At the **Randomization/Treatment EEC Session One (Visit 3)**, qualified site staff will update concomitant medications, collect AEs, as applicable and collect vital signs. A urine pregnancy test will be administered to WOCBP. Ophthalmic evaluations will be conducted (Fundus exam, Snellen VA, NCT SLE, subject rating of symptoms, and staff grading of conjunctival redness). [REDACTED]

Subjects will be randomized to receive a first dose of either Reproxalap Ophthalmic Solution (0.25%) (Treatment A) or Vehicle Ophthalmic Solution (Treatment B). Qualified site staff will instill one drop of the randomized treatment into each eye at approximately time zero [REDACTED] prior to entry to the EEC after all the pre-EEC assessments are done.

Visit 3 Pre-EEC entry (Baseline):

- 1) Subject assessment for ocular itching and tearing will be recorded [REDACTED] and [REDACTED]
- 2) Staff-assessed conjunctival redness will be recorded [REDACTED].

Visit 3 Post-EEC entry:

- 1) Subject assessment for ocular itching and tearing will occur [REDACTED].
- 2) Staff-assessed conjunctival redness will be recorded [REDACTED].

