2.2 Sample Size

Approximately 670 subjects with ragweed-induced, moderate-to-severe allergic conjunctivitis will be screened in the EEC in order to randomize approximately 126 subjects, and for 100 subjects to

complete the study. Approximately sixty-three (63) subjects will be assigned to each of two (2) treatment sequences, AB and BA.

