6.1 General Statistical Procedures

Frequency distributions for categorical variables will be provided as number of patients in the category and the percentages of the total number of patients in the given population as noted. Percentages will be reported to one decimal place.

The descriptive statistics for continuous variables will be number of subjects (n), mean, standard deviation (SD), median, minimum and maximum. Mean and median will be reported to 1 more decimal place than the raw data, while the SD will be reported to 2 more decimal places than the raw data. Minimum and maximum will be reported the same as the original data.

All statistical tests will be two-sided with a significance level of 0.05 ($\alpha = 0.05$) unless otherwise specified. Confidence interval (CI) for differences between treatment will be two-sided at 95% confidence interval.

P-value will be rounded to at most 3 decimal places and will be reported as < 0.001 if it is smaller than 0.001.

Unless otherwise specified, subjects' characteristics at baseline will be summarized by treatment sequences (Reproxalap 0.25%/Vehicle, Vehicle/Reproxalap 0.25%). Safety and efficacy will be summarized by treatment (Reproxalap 0.25%, Vehicle) where appropriate.

In general, all listings will be ordered by subject number and visit for available data unless otherwise specified in the text.

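### SAP 7.2 counts an adverse event as ocular only if it is coded to eye disorders, so an eye event coded to another organ class would be tabulated as non-ocular

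*SAP*

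**What the plan says.** SAP 7.2 (Adverse Events) defines the ocular category by coded organ class: "An AE is classified as an ocular AE if system organ class is coded as eye disorders". The overall summary then has ocular rows for any, drug-related, serious and discontinuation events. Each type of table comes in three forms: all events, ocular and non-ocular, for example "Non-Ocular TEAEs by SOC and PT". The non-ocular category has no definition of its own. The layout instruction covers every one of these tables: "Summaries will be sorted by decreasing frequency of PT within SOC which will be sorted alphabetically".

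Protocol 10.8 (Safety Analysis) also plans a separate ocular analysis but does not say what makes an event ocular. Protocol 10.3 states that the SAP "will detail all planned analyses and will dominate any statistical analysis herein", so the SAP sentence is the working definition. The two documents do not conflict on this point.

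Both products are given directly to the eye. SAP 2.1 states: "Qualified site staff will instill one drop of the randomized treatment into each eye".

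**The concern.** Local tolerability is a main safety question for an eye drop, and both documents set aside a separate ocular analysis to answer it. Organ class and site of event are different things. An event can occur at the eye and still be coded by its nature (for example as an infection, an injury, a measurement or an administration-site reaction) under another class. If that happens, the ocular tables omit it and the non-ocular tables contain it.

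The error can run only one way. Compared with a definition that also admits events by site, the SAP rule can reduce the ocular counts but never increase them. That applies equally to the drug-related, serious and discontinuation rows. Other defaults in SAP 7.2 lean towards caution: a missing relationship counts as related and a missing severity counts as severe. This rule leans the other way.

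**Working it through.** The plan states no figure for this point. The check is a reading of the rule, a count of the outputs that depend on it, and the effect of one subject.

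**Step 1. Is there another route to ocular?** The sentence says if, not only if, so the rest of the text matters.
- SAP 7.2 has no site or laterality criterion, no list of preferred terms and no review of the classification. Its one redaction is in the coding-dictionary sentence, ahead of the rule.
- Protocol section 9 describes sight-threatening serious events by damage to the eye (9.1.3) but sets no classification for the tables.
- Protocol 10.8 plans the ocular analysis without defining it.
- SAP 7.1 summarises eye examinations by eye and side, but that concerns examination results, not adverse events.

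No visible text supplies a second route, and non-ocular can only be the complement.

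**Step 2. Consequence.** An eye-site event coded outside eye disorders fails the one test. It leaves the ocular outputs and enters the non-ocular ones. A side effect is that every ocular table arranged by organ class can hold only one class, so the class ordering does nothing there.

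**Step 3. Outputs that depend on the rule (counted in SAP 7.2).**

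| Output | Total | Depends on the rule | Does not |
|---|---|---|---|
| Overall-summary rows | 8 | 4 ocular | 4 all-event |
| Tables: 5 types × 3 forms | 15 | 5 ocular + 5 non-ocular = 10 | 5 all-event |
| Adverse event listings | 3 | 0 | 3 |

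The 5 types are: by class and term, by causality, serious, by maximum severity, and leading to discontinuation.

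**Step 4. Effect of one subject.** Change in a treatment's any-ocular percentage = 100 × k / N. Here k is the number of subjects whose only eye-site event on that treatment is coded elsewhere, and N is the denominator.
- SAP 6.1 gives the denominator only as "the percentages of the total number of patients in the given population as noted". N is assumed to lie between the planned completers and the planned randomized number in SAP 2.2: "in order to randomize approximately 126 subjects, and for 100 subjects to" complete.
- k = 1: 100 × 1/126 = 0.79 point; 100 × 1/100 = 1.00 point.
- For scale only, at N = 126: k = 3 gives 100 × 3/126 = 2.4 points, and k = 6 gives 100 × 6/126 = 4.8 points.

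The documents give no adverse event rates and no coded terms, so k cannot be estimated. These values of k are illustrations, not forecasts.

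**The case against.** The strongest reply is that the documents do not show any harm. They do not reproduce the coding dictionary, so nothing in them proves that an eye-site event would be coded outside eye disorders, or how often. This stands as a limit on size: the effect may be zero. It does not remove the point, because the claim is conditional and the rule makes no provision for such an event.

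A second reply is that the rule is prespecified, mechanical and reproducible, and that the protocol leaves the definition to the SAP. That is a real advantage, and the remedy gives up a little of it.

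Third, the information stays visible. Every event remains in the all-event tables and the listings, the non-ocular tables show preferred terms, and visual acuity, slit lamp, pressure and fundus results are summarised separately under SAP 7.1. Protocol 9.1.1 also restricts when an abnormal finding becomes an adverse event, which limits how many pressure findings could be affected. All of this is correct and keeps the point minor. But a reader who relies on the ocular table, which exists so that the eye can be judged separately, would still see an incomplete count.

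Finally, the SAP contents list an appendix that is not in the available text, so a wider rule there cannot be excluded. Nothing in SAP 7.2 refers to one.

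**Conclusion.** The concern holds as a cheap improvement. As written, the eye disorders class is the only stated test for an ocular event, and an eye-site event coded elsewhere would be reported as non-ocular. The exposed outputs are 4 of 8 summary rows and 10 of 15 tables. Each affected subject lowers the any-ocular percentage for that treatment by 0.8 to 1.0 point. The total runs from zero to unknown.

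This rests on two assumptions. The denominator is taken to lie between 100 and 126. Which terms might be coded elsewhere (possibly instillation-site reactions, pressure findings, eye infections or eye injuries) is a matter of dictionary coding that the documents do not settle. If no such event occurs, the tables are the same under either definition. All-event counts, the listings and the efficacy results are unaffected in every case.

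**What to change.** Replace the sentence in SAP 7.2 with a two-part definition. An adverse event is ocular if (a) its system organ class is eye disorders, or (b) it is coded to another class but its site is the eye, including instillation-site terms following the eye drops. All other events are non-ocular. Group (b) is flagged by a masked review of the coded terms and fixed before database lock.

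The cost is a short SAP edit and a brief term review. The adverse event attributes listed in Protocol 9.1.1.3 include no site or side, so the reviewer may have to infer site from the reported term. A line saying how unclear terms are handled would keep the review consistent. The downsides are that some judgement replaces a purely mechanical rule and that reported ocular rates may be higher.
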